7.1 Baseline

Baseline is defined as the last non-missing observation made before the study treatment administration.

7.2 Data consideration

Not Applicable

7.3 End of study

Day 30 is the end of study day.

7.4 Stratifications

For analysis purposes, trial participants may be sub-classified into the following stratification levels, where applicable:

- **Groups for Part-1 (Fasting):**
 - Group 1 (PQP Hard Tablet)
 - Group 2 (PQP Dispersible Granules)
- **Groups for Part-2 (PQP Dispersible Granules - Fed):**
 - Group 3 (High-fat Meal)
 - Group 4 (Low-fat Meal)
 - Group 5 (Whole Milk 250ml)

7.5 Statistical tests

No formal tests will be applicable for the safety analysis.

7.6 Interim analysis

No formal interim analysis is planned for this study, other than the safety/PK report that will be performed for the SRC review during the transition from Part 1 to Part 2.

7.7 Common calculations

For quantitative measurements, change from baseline will be calculated as: (Test value at Visit Day X – Baseline value), where the baseline value is defined as the last non-missing observation made before first study treatment administration.

7.8 Software

All statistical analyses will be conducted using SAS® Version 9.4 or higher.

8. Statistical considerations**8.1 Multicenter studies**

Not applicable.

8.2 Missing data

All data will be inspected for potential errors and a summary of missing data will be generated including the percentages of those with non-missing data, dropouts, and replacement of participants. Unrecorded values will be treated as missing. Missing values will not be imputed and will be reported in the listings as either "missing" or as the justification for the value being missing e.g., "ND" (not detected), where appropriate.

For adverse event, prior and concomitant medication data, partial date imputations will be performed where at least the year is provided.

9. Output presentations

The templates provided in the separate output templates document describe the format and content for the presentation of tables, listings, and figures (TLFs).

For continuous measures, summary statistics will include the number of participants (n), number of missing values, mean, standard deviation (SD), median, minimum, and maximum for both the actual and the change from baseline measurements. For categorical measures, summary statistics will include the number of participants (n), number of missing values and percentages.

All percentages (%) for a specific summary are calculated using the total number of participants included in the relevant analysis population as the denominator unless otherwise specified.

10. Participant disposition and withdrawal

The following analysis will be applicable to both, part-1, and part-2 of the study.

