### 10.5 Analysis sets

The analysis of data will be based on different analysis sets according to the purpose of analyses. Participant eligibility for each analysis set will be finalised before the database hard lock.

The Safety analysis set will consist of all randomized participants who received at least one dose of the IMP.

The PK analysis set will consist of those participants in the safety set who have sufficient blood samples taken for at least one of the PK variables to be calculated.

In all populations, analyses will be based on the treatment received, regardless of the randomization (any such deviations will be reported). A participant who withdraws prior to the last planned observation in a trial period will be included in the analyses up to the time of discontinuation.

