16.2 Analysis

Population: Table: SAF

Listing: ENRL

Stratification: Table: By part and group

Listing: By part, group, participant, timepoint & parameter

Statistics: Summaries of all the laboratory tests will include descriptive statistics at each assessment of the following:

- Actual and change from baseline (number of participants, mean, SD, median, minimum & maximum) (for quantitative measurements) for which baseline data is collected. i.e., Biochemistry, Hematology.
- Frequencies and percentages (n and %) (for qualitative measurements). i.e., Thick blood smear – Malaria, Pregnancy test, Urinalysis, Urine for drugs of abuse, Alcohol breath test.)

Qualitative laboratory measurements will be compared with the relevant laboratory reference ranges and summarized as:

- Normal: Within the laboratory reference range (upper and lower limit included)
- Abnormal NCS: Abnormal not clinically significant
- Abnormal CS: Abnormal clinically significant
- High: Higher than the upper limit of the reference range
- Low: Lower than the lower limit of the reference range

Above categorizations and abnormal laboratory data will be flagged and presented in data listings.

The qualitative urinalysis data will be listed only. Those above lab parameters that will only be done in screening will be listed only.

17. 12-Lead ECG & Vital signs

The following analysis will be applicable to both, part-1, and part-2 of the study.

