17.2 Analysis

Population: Table: SAF

Listing: ENRL

Stratification: Table: By part and group

Listing: By part, group, participant, timepoint & parameter

Statistics: Summaries of all 12-Lead ECG & vital parameters will include descriptive statistics at each assessment of the following:

- Actual and change from baseline (number of patients, mean, SD, median, minimum & maximum) (for quantitative measurements)
- Frequencies and percentages (n and %) (for qualitative measurements)

"Any Clinically Significant Abnormality Found in Vital Signs" will be found as "Yes" on the eCRF page of Vital signs, it will be summarized as Frequencies and percentages (n and%).

In ECG analysis, if triplicate ECG performed then the average of three repetitions will be calculated and used for the further evaluation.

The qualitative measurements of ECG will be categorised as (Normal, Abnormal Clinically Significant and Abnormal Not Clinically Significant) Above categorizations and abnormal data will be flagged and presented in data listings.

Additionally, QTcF data will be summarized using frequencies & percentages (n and %) as follows:

Absolute QTcF interval prolongation

- QTcF interval > 450 ms
- QTcF interval > 480 ms
- QTcF interval > 500 ms

Change from baseline in QTcF interval

- QTcF interval increases from baseline > 30 ms
- QTcF interval increases from baseline > 60 ms

The mean value of change from baseline QTcF parameters will be plotted by group and time point.

18. Primary Endpoint Analysis

18.1 To determine the relative bioavailability of a single oral dose of PQP dispersible granule formulation (Test) as compared to PQP hard tablet formulation (Reference) in the fasted state.

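### By default, per-visit ECG, QTcF and laboratory percentages are divided by the whole safety set, so any missing value lowers the printed abnormality rate

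*SAP*

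**What the plan says.** The default denominator is in SAP section 9 (Output presentations): percentages are "calculated using the total number of participants included in the relevant analysis population as the denominator unless otherwise specified". The closing words allow exceptions.

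SAP 16.2 (laboratory) and 17.2 (ECG and vital signs) build their tables on the safety set, meaning everyone randomized and dosed. Both call for frequencies and percentages of qualitative results at each assessment. For QTcF, section 17.2 adds: "Additionally, QTcF data will be summarized using frequencies & percentages (n and %) as follows". The categories are absolute values above 450, 480 and 500 ms and increases above 30 and 60 ms. Neither section names a denominator. Section 17.2 does not say whether a participant is classified at each time point or once over all post-dose ECGs, and the planned table title in Appendix 3 (Summary of QTcF by Parts) does not settle it.

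On missing data, SAP 8.2 and 9 say:
- "Missing values will not be imputed and will be reported in the listings"
- "a summary of missing data will be generated including the percentages of those with non-missing data"
- "For categorical measures, summary statistics will include the number of participants (n), number of missing values and percentages"

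Protocol 10.5 adds that a participant who withdraws early "will be included in the analyses up to the time of discontinuation".

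**The concern.** The whole safety set is the right denominator for adverse event incidence, where everyone dosed is under observation and no report means no event recorded. It suits a measurement category at a visit less well. If the ECG or sample was not taken, the participant's status is unknown, but the default leaves that person in the denominator with no chance of entering the numerator. After a withdrawal this recurs at every later visit.

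Mean change in QTcF at a visit can only use observed values. A mean and a category percentage for the same visit could therefore rest on different numbers of participants.

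The stake is QTc. Protocol 2.1.5 describes a concentration-related QTc effect, with a mean prolongation of 15–20 ms in the fasted state, and Part 2 doses participants with food. For abnormality categories the dilution runs in one direction, towards apparent safety. If missingness differs between groups of 12, it also distorts the descriptive comparison between them.

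**Working it through.** **Inputs**
- N = 12 per group (SAP 4.3).
- Denominator = N by default (SAP 9); no imputation (SAP 8.2).
- x = participants in the category, m = participants with no value. The documents give neither, so both are assumptions here.
- The plan states no QTcF rate or missing-data rate, so there is no figure of its own to reproduce.

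**Formulas**
- Printed rate: x/N.
- Rate among those measured: x/(N−m).
- Ratio of printed to measured: (N−m)/N.
- Possible range for all N participants: from x/N (no missing participant in the category) to (x+m)/N (all of them in it).

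**Results for x = 2, N = 12**

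| m | Printed | Among measured | Difference | Ratio | Possible range |
|---|---|---|---|---|---|
| 0 | 2/12 = 16.7% | 2/12 = 16.7% | 0 | 1 | 16.7% |
| 1 | 2/12 = 16.7% | 2/11 = 18.2% | 1.5 points | 11/12 = 0.917 | 16.7% to 25.0% |
| 2 | 2/12 = 16.7% | 2/10 = 20.0% | 3.3 points | 10/12 = 0.833 | 16.7% to 33.3% |
| 3 | 2/12 = 16.7% | 2/9 = 22.2% | 5.6 points | 9/12 = 0.750 | 16.7% to 41.7% |

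The printed figure is always the bottom of the possible range. On these assumptions, a group with 2 of 12 measured above a threshold and a group with 2 of 9 measured above it would both print 16.7%.

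**Are missing participants classed as normal?** Take x = 2 and m = 1. The plan gives 2/12 = 16.7% prolonged, (12−1−2)/12 = 75.0% not prolonged, and 1 participant (8.3%) missing. Classing the missing participant as normal would give 10/12 = 83.3% not prolonged. The plan does not produce that figure, and the normal share is diluted in the same way as the abnormal share.

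**A case that needs no missing data.** SAP 16.2 lists the pregnancy test among the results summarized by frequency and percentage in the safety set. Protocol 7.2 limits that test to women of childbearing potential, Protocol 7.3.2.1 repeats it on Day -1 (so it is not a screening-only test), and men are enrolled. If w of a group's 12 participants are eligible for the test and all are negative, the default prints w/12 negative rather than 100%.

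**The case against.** The strongest reply is that x/N is not an error. It is the proportion of the safety set with observed prolongation, N appears in the column header under SAP 22.3, and the number missing is printed, so a reader can recompute. If the unmeasured participants were not prolonged, x/N is exact and x/(N−m) overstates. If people leave because of an adverse event, the measured-only rate is not unbiased either. This stands, and it is why the printed figure is called a lower bound here and not simply a biased estimate. It does not make the full set the better default for a per-visit table, because a printed missing count does not change the tabulated rate.

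Other parts of the reply also hold:
- The rule allows exceptions, and SAP 9 places table format and content in a separate templates document that is not available. It may set another denominator. On the text provided, the default applies.
- If QTcF categories are counted once over all post-dose ECGs, a participant who misses one visit still contributes through the others, and the effect is small.
- Missing ECGs are least likely when concentrations are highest. Protocol 2.1.3 puts Tmax at about five hours after the tablet, and ECGs to about 48 hours are taken in-house.
- Safety has no formal tests (SAP 7.5). The counts of out-of-range laboratory and vital-sign values promised in Protocol 10.6 are unaffected by any denominator.
- Protocol 10.5 governs which data of a withdrawn participant are used. A fixed denominator at later visits fits poorly with it but does not contradict it.

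A reader might infer that the plan counts a missing ECG or laboratory result as normal. The documents do not support this. Nothing is imputed, missing counts are shown, and the laboratory category is defined as "Normal: Within the laboratory reference range (upper and lower limit included"), which needs an observed value. No ECG category absorbs missing results.

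**Conclusion.** The point holds as a minor one. By default, and with no exception in SAP 16.2 or 17.2, per-visit percentages for ECG and laboratory categories use the full safety set; the same applies to QTcF categories if they are tabulated by visit. With m of 12 values missing, the printed rate is (12−m)/12 of the rate among those measured: 0.917, 0.833 and 0.750 for m = 1, 2 and 3. With 2 events, the printed rate is 1.5, 3.3 and 5.6 percentage points lower. The event and missing counts are illustrative assumptions. With complete data the effect is zero, apart from the pregnancy test, where ineligible participants stay in the denominator regardless.

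Two wider readings go too far. The rule does not bind every percentage in the report, because it yields to any other specification. Nor are QTcF rates biased downward in general: that requires missing values and prolongation among the participants not measured, and it matters mainly in per-time-point tables. No planned inference depends on these percentages.

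**What to change.** Add denominator rules to SAP 16.2 and 17.2, with a cross-reference in section 9:
- Per-visit categories: participants with a non-missing value at that visit.
- Change-from-baseline categories: participants with both a baseline value and a value at that visit.
- Pregnancy test: only participants to whom the test applies.
- QTcF: state whether categories are per time point or worst post-dose; for the latter, divide by participants with at least one post-dose value (and a baseline value for the change categories).
- Adverse event incidence: keep the full safety set.

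The cost is a sentence or two in the SAP and a denominator change in the table programs. The downside is that denominators will vary by visit, so each must be printed beside its percentage; the number missing should stay in the table.

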10.1 Variables and derivations

The following parameters will be summarized for the participant's disposition table as per eCRF:

- Number of screened participants
- Number of screening failure participants
- Number of enrolled participants
- Number of participants screened but discontinued before randomization.
- Number of randomized participants*
- Number of study completed participants.
- Number of study discontinued participants.
- Reasons for study discontinuation
- Number of participants in the Safety analysis set.
- Number of participants in the PK analysis set.

*Randomized: Participants who are screen positive and assigned to the treatment.

Screening Failure: Participants who did not meet any Inclusion/ Exclusion Criteria or Are not eligible for the trial.

10.2 Analysis

Population: ENRL

Stratification: Table: By part and group

Listing: By part, group and participant

Statistics: All above mentioned participant's disposition parameters, will be summarised (frequency & percentage) and participants listing for all participants by participant number will be provided.

The reasons for study discontinuation will be summarized as per eCRF end of study form.

The summary for safety and PK analysis set will be presented with their exclusion reason from respective analysis set and listing with population assignment and exclusion reason will be provided.

Summary for protocol deviation will be presented by category (i.e., Major/Minor) and participant data listing will be provided by participant number.

11. Participant demographics and other baseline characteristics

The following analysis will be applicable to both, part-1, and part-2 of the study.

11.1 Variables and derivations

The following demographic and other baseline characteristics will be summarized:

- Age (Years)
- Sex
- Race
- Ethnicity
- Height
- Weight
- BMI

11.2 Analysis

Population: Table: SAF and PK

Listing: ENRL

Stratification: Table: By part and group

Listing: By part, group and participant

Statistics: Baseline and Demographic variables will be summarized for each stratification factor and overall, also listed by participant number. The summaries will include descriptive statistics for continuous measures (number of participants, number of missing values, mean, SD, median, minimum & maximum) and for categorical measures (frequency, percentages, and number of missing values).

12. Exposure to IMP**12.1 Analysis**

Population: SAF

Stratification: Table: By part and group

Listing: By group and participant

Statistics: Planned dose and actual dose will be summarized descriptively (number of participants, number of missing values, mean, SD, median, minimum & maximum). Study drug administration information will be listed by participant number.

13. Medical history summary

The following analysis will be applicable to both, part-1, and part-2 of the study.

13.1 Analysis

Population: SAF

Stratification: Table: NA

Listing: By group and participant

Statistics: Medical history data will be listed by participant number.

14. Prior, concomitant, and other medications

The following analysis will be applicable to both, part-1, and part-2 of the study.

14.1 Variables and derivations

Concomitant medications will be coded using the WHO-DD, dated 1 March 2023, or higher.

Prior medications are defined as any medication taken before the first administration of the study treatment.

'Concomitant medications' are defined as any medication taken after the first administration of the study treatment.

In section 23 of Appendix 1, the algorithm is given for the calculation of partial date imputation for prior and concomitant medications, and it will be used for partially missing prior and concomitant medications, start and end date imputation.

The following parameters will be summarised for concomitant medications:

- Number of participants with at least one prior and concomitant medication
- Number of participants for each prior and concomitant medication by ATC and PT.

14.2 Analysis

Population: Table: SAF

Listing: ENRL

Stratification: Table: By part and group

Listing: By part, group and participant

Statistics: Prior and Concomitant medication will be summarized (frequency, percentages) by group and a listing will be presented.

15. Adverse events

The following analysis will be applicable to both, part-1, and part-2 of the study.

15.1 Variables and derivations

Adverse Events (AEs) will be coded using MedDRA central coding dictionary, version 26.0 or higher.

For the definition of Adverse events (AE) and Serious adverse events (SAE) refer to the protocol sections 8.1.2 & 8.4.

Pre-treatment adverse-events are defined as AEs between informed consent and IMP administration.

Treatment-emergent adverse events (TEAEs) are defined as an event that emerges during treatment, have been absent pre-treatment or worsens relative to the pre-treatment state.

The following parameters will be summarised for the participant's adverse events as mentioned in eCRF:

- All Adverse Events
- Number of participants with at least one Pre-Treatment AE
- Number of participants with at least one TEAE
- Number of participants with at least one study drug-related TEAE
- Number of participants with at least one serious TEAE
- Number of participants with at least one study drug-related serious TEAE
- Ongoing AEs
- TEAEs by Toxicity Grade
- TEAEs by Outcome
- TEAEs by Action Taken with Study Treatment
- TEAEs by Relationship
- TEAEs leading to Death.
- TEAEs leading to withdrawn or discontinued the study.

Derivations:

- The question on eCRF page Adverse Events "Relationship to investigational product" is answered "Related/Suspected", then respective AEs will be considered as drug-related AEs.
- If The question on eCRF page Adverse Events "Was the adverse event serious" is answered as "YES" then the respective AE will be considered as serious AE.
- The question on eCRF page Adverse Events "Was the adverse event serious" is answered as "YES" and answered as "Related/Suspected" then respective AEs will be considered drug-related SAEs.

- If the seriousness criteria are “RESULTS IN DEATH” then we will consider it as AE leading to death.
- participant’s primary reason for discontinuation is “ADVERSE EVENT” then we will consider it as AE leading to withdrawal/discontinued from the study.

Imputations will only be performed where at least the year is provided. The imputations derived for partial dates will be as per appendix 1.

15.2 Analysis

Population: Table: SAF

Listing: ENRL

Stratification: Table: By part and group

Listing: By part, group and participant

Statistics: An overall summary will be presented as the number of participants within each of the event type categories described in the sub-sections below, including the incidence of AEs by system organ class (SOC) and preferred term (PT) sorted by decreasing frequency within the SOC and PT. The number of participants with AEs will be presented. Both number of participants, number of events (One participant may be counted more than once) and percentage will be provided.

The Adverse Event will be summarized and presented in data listings with all AEs (including coding details SOC and PT) and participants with SAEs, death, and events resulting in study discontinuation will be listed separately by participant number.

Treatment-emergent AEs (TEAE) will be summarized for all participants by SOC and PT. Each TEAE will be counted only once for a given participant. If the same TEAE occurs on multiple occasions, the highest severity and relationship will be assumed. A summary of serious TEAE will be presented separately. All other TEAEs will be summarized similarly.

Note: If there are uncoded adverse events, then the uncoded category will be added to the AEs by SOC/PT summary tables.

15.2.1 Incidence of Pre-Treatment AEs

The incidence of all AEs by SOC and PT will be presented.

15.2.2 Incidence of TEAEs (all causalities)

The incidence of all TEAEs by SOC and PT will be presented.

15.2.3 TEAEs by Toxicity Grade

The incidence of all AEs by SOC, PT, and toxicity grade will be presented.

15.2.4 TEAEs by Outcome

The incidence of all AEs will be presented by SOC, PT, and outcome.

15.2.5 TEAEs by Action Taken

The incidence of all TEAEs will be presented by SOC, PT, and action taken.

15.2.6 Drug-Related TEAEs

The incidence of all drug-related TEAEs will be presented by SOC and PT.

15.2.7 Drug-Related TEAEs by Severity

The incidence of all drug-related TEAEs will be presented by SOC, PT and severity.

15.2.8 Serious AEs and Serious TEAEs

The incidence of all serious AEs and TEAEs will be presented by SOC and PT.

15.2.9 TEAEs and SAEs leading to withdrawal/discontinuation from the study

The incidence of all TEAEs and SAEs leading to withdrawal/discontinuation will be presented by SOC and PT. A data listing of TEAEs and SAEs leading to withdrawal/discontinuation from the study will be presented.

